Rationale for the study and study design	
 • Rationale for the study 
Recent studies have shown that maternal combined reduced antigen content diphtheria-tetanus-acellular pertussis (dTpa) vaccination during pregnancy results in high pertussis antibody concentrations in infants during the period between birth and the first vaccine dose of Diphtheria-Tetanus-acellular Pertussis (DTPa) vaccination series. Although slightly decreased immune responses following the primary DTPa vaccination has been observed in infants whose mothers received dTpa vaccine compared to those whose mothers did not receive dTpa vaccine, the differences did not persist following the booster vaccination in infants [Hardy-Fairbanks, 2013; Gall, 2011].
 
An analysis of data from the Clinical Practice Research Datalink (a primary care database of 520 general medical practices in England) demonstrates that maternal dTpa immunisation can decrease the incidence of infant pertussis. After a maternal pertussis vaccination programme was introduced in October 2012 in response to a pertussis outbreak in England, the number of pertussis cases in infants younger than three months of age and the number of hospitalisations decreased significantly [Amirthalingam, 2014]. (Amended 06 September 2016)
 
In 2013, the Advisory Committee on Immunisation Practices (ACIP) recommended that all women should be vaccinated with dTpa vaccine during each pregnancy, regardless of the previous immunisation schedule [CDC, 2013b]. Similar recommendations have been implemented in many countries including UK, New Zealand, Israel, Mexico, Brazil, Colombia, Uruguay, Panama, Costa Rica, Argentina and some provinces in Australia and Spain [Joint Committee on Vaccination and Immunisation (JCVI), 2012; Pharmaceutical Management Agency (PHARMAC), 2012; TAG, 2013]. The National Advisory Committee on Immunisation in Canada

recommends that all pregnant women following 26 weeks of pregnancy who have not received a dose of pertussis-containing vaccine in adulthood should be encouraged to receive *dTpa* vaccination. In special circumstances, such as an outbreak situation, all pregnant women who are of 26 weeks gestation or greater may be offered *dTpa* vaccination irrespective of their immunisation history [Warshawsky, 2014; Public Health Agency of Canada, 2014]. (*Amended 06 September 2016*)

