1. INTRODUCTION

1.1. Background

Infants experience the highest rates of serious complications, hospitalisations and death due to pertussis. This is mainly because they are too young to have completed the primary diphtheria, tetanus and acellular pertussis (DTPa) immunisation series.

Since 2000, most deaths and hospitalisations related to pertussis have been in unvaccinated infants younger than three months of age [Murphy, 2008]. In 2012, there were 48,777 reported cases of pertussis in the United States (US). Infants younger than one year of age had the highest incidence compared to other studied age groups. Fifteen out of 20 deaths occurred in unvaccinated infants younger than three months of age. In 2013, there were 24,231 reported cases of pertussis in the US. The incidence again was highest in infants younger than one year of age and all of nine deaths due to pertussis occurred in unvaccinated infants three months of age and younger [CDC, 2013a; CDC, 2013b].

In Canada, approximately 2500 cases were reported in 2012 [Public Health Agency of Canada, 2012]. The United Kingdom was amidst a large outbreak of pertussis in 2012. A national increase in the laboratory-confirmed cases of pertussis has also been observed in England and Wales, with a large number of cases being reported in very young infants [Health Protection Report, 2012]. The number of pertussis cases reported in Australia has also been increasing with nearly 40,000 cases reported in 2011 and 2012. While the rates are highest in the primary school-aged children, due to the waning of vaccine-induced immunity, the impact of the disease remains greatest in infants under one year of age [Communicable Disease Control Directorate, 2011].

Transplacental transfer of maternal antibodies is considered to provide some degree of protection to infants in the first few months of their life. Unfortunately, low levels of the maternal antibodies and rapid decay of the antibodies in the infants often leave them at high risk for pertussis. One way to confer protection to infants is to immunise mothers late during pregnancy. This concept of “boosting” maternal levels of antibody to pertussis has been suggested as early as 1995. However, the findings that pre-existing high levels of pertussis antibody in infants suppress the ultimate immune response to whole-cell diphtheria, tetanus and pertussis (DTP) vaccines lessened the enthusiasm for this approach [Englund, 1995].

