In line with these recommendations, study 116945 [DTPA (BOOSTRIX)-047] will be conducted to evaluate the immunogenicity and safety of GlaxoSmithKline (GSK) Biologicals' dTpa vaccine, *Boostrix*, in pregnant women, ***as well as the transfer of maternal antibodies against pertussis to the foetus (cord blood sample at delivery)***. Subjects will receive a dose of *Boostrix* during pregnancy or immediately post-delivery. **(Amended 06 September 2016)**

All infants born to pregnant women who participate in study 116945 [DTPA (BOOSTRIX)-047] will be offered enrolment in the present study. This study will be conducted to evaluate the immunogenicity and safety of GSK Biologicals' combined diphtheria-tetanus-acellular pertussis-hepatitis B-inactivated poliovirus and *Haemophilus influenzae* type b vaccine (DTPa-HBV-IPV/Hib), *Infanrix hexa*, given in the primary vaccination schedule. This will help us evaluate if the presence of transplacentally transferred maternal antibodies interfere with the immune response to primary vaccination with *Infanrix hexa* and a co-administered pneumococcal conjugate vaccine given as a part of this study in infants.

The following section outlines the risk assessment and mitigation strategy for this study protocol:

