4. ENDPOINTS

4.1. Primary endpoints

- Immunogenicity with respect to components of *Infanrix hexa*.
 - Anti-diphtheria, anti-tetanus, anti-HBs, anti-poliovirus type 1, anti-poliovirus type 2, anti-poliovirus type 3 and anti-polyribosyl-ribitol phosphate (anti-PRP) seroprotection status, one month after the last dose of primary vaccination.

A seroprotected subject is a subject whose antibody concentration/titre is greater than or equal to the level defining clinical protection. The following seroprotection thresholds are applicable:

 - Anti-diphtheria antibody concentrations ≥ 0.1 IU/mL.
 - Anti-tetanus antibody concentrations ≥ 0.1 IU/mL.
 - Anti-HBs antibody concentrations ≥ 10 mIU/mL.
 - Anti-poliovirus types 1, 2 and 3 antibody titres ≥ 8 .
 - Anti-PRP antibody concentrations ≥ 0.15 $\mu\text{g/mL}$.
 - Vaccine response to PT, FHA and PRN antigens, one month after the last dose of primary vaccination.

Vaccine response to the PT, FHA and PRN antigens, is defined as:

- appearance of antibodies in subjects who were initially seronegative (i.e., with concentrations $<$ cut-off value).
- at least maintenance of pre-vaccination antibody concentrations in subjects who were initially seropositive (i.e., with concentrations \geq cut-off value).

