2080	
Vaccination done but: noncompliance with vaccination schedules (dates of vaccination not corresponding to protocol intervals or unknown vaccination dates)
 
Intervals between study visits for subjects vaccinated with Infanrix hexa at 2, 4 and 6 months of age is 42-104 days from birth to visit 1, 52-78 days from visit 1 to visit 2, 52-78 days from visit 2 to visit 3.
 
Intervals between study visits for subjects vaccinated with Infanrix hexa at 2, 3 and 4 months of age is 42-104 days from birth to visit 1, 21-48 days from visit 1 to visit 2, 21-48 days from visit 2 to visit 3.
 
Intervals between study visits for subjects vaccinated with Infanrix hexa at 2 and 4 months of age is 42 to 104 days from birth to visit 1, 52-78 days from visit 1 to visit 2.
 
Intervals between study visits for subjects vaccinated with Infanrix hexa at 3 and 5 months of age is 42 to 104 days from birth to visit 1, 52-78 days from visit 1 to visit 2.

2090	
Blood sample taken but: noncompliance with blood sampling schedules (dates of blood sampling not corresponding to adapted protocol intervals or unknown blood sample/vaccination dates) => 21-48 days from last vaccination visit to visit 4

2100	
Serological results not available for antigens POST vaccination (including lost samples, blood sample not done, unable to test, absence of parallelism) => no immunogenicity results available at visit 4.

2120	
Obvious incoherence, abnormal serology evolution or error in data (incoherence between CRF and results, wrong sample labelling)

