6.3.2. Additional considerations

Considering that RCC are available and the percentage of subjects with titres/concentration above key thresholds are available, the distribution of antibody concentrations or titres of each antigen will not be tabulated.

In addition to the percentage of seroprotected or seropositive subjects, the percentage of subjects above the following cut-off will be summarized

- Anti-PRP antibody concentrations $\geq 1.0 \mu\text{g/mL}$.
- Anti-diphtheria antibody concentrations $\geq 1.0 \text{ IU/mL}$.
- Anti-tetanus antibody concentrations $\geq 1.0 \text{ IU/mL}$.
- Anti-HBs antibody concentrations $\geq 100 \text{ mIU/mL}$.
- Anti-pneumococcal serotypes (1, 3, 4, 5, 6A, 6B, 7F, 9V, 14, 18C, 19A, 19F, 23F) $\geq 0.35 \mu\text{g/mL}$.

In light of the number of subjects enrolled in each country, the analysis by country will be replaced with analysis by schedule (2 doses ie 2,4 months combined with 3,5 months versus 3 doses i.e. 2,3,4 months combined with 2,4,6 months).

In addition subgroups analysis according to gestational age (27-32 weeks and 33-36 weeks) and age of the mother (18-24 year, 25-34 year and 35-45 year) will be performed.

The sub-group analyses will be limited to descriptive tables of GMT/GMC and the percentage of subjects with titres/concentration above key thresholds for ATP cohort of immunogenicity.

SCHEDULE_TXT(Element Text)	country(CTY_NAM)						Total
Frequency Percent Row Pct Col Pct	Australia	Canada	Czechia	Finland	Italy	Spain	
Age group(2, 3, 4 Months)	0 0.00 0.00 0.00	0 0.00 0.00 0.00	71 11.81 100.00 100.00	0 0.00 0.00 0.00	0 0.00 0.00 0.00	0 0.00 0.00 0.00	71 11.81
Age group(2, 4 Months)	0 0.00 0.00 0.00	0 0.00 0.00 0.00	0 0.00 0.00 0.00	0 0.00 0.00 0.00	0 0.00 0.00 0.00	7 1.16 100.00 2.48	7 1.16
Age group(2, 4, 6 Months)	38 6.32 8.32 100.00	144 23.96 31.51 100.00	0 0.00 0.00 0.00	0 0.00 0.00 0.00	0 0.00 0.00 0.00	275 45.76 60.18 97.52	457 76.04
Age group(3, 5 Months)	0 0.00 0.00 0.00	0 0.00 0.00 0.00	0 0.00 0.00 0.00	52 8.65 78.79 100.00	14 2.33 21.21 100.00	0 0.00 0.00 0.00	66 10.98
Total	38 6.32	144 23.96	71 11.81	52 8.65	14 2.33	282 46.92	601 100.00

Deviations from specifications for age and intervals between study visits for subjects vaccinated with *Infanrix hexa* by dose schedule (2 dose schedule and 3 dose schedule separately) will be tabulated.

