dTpa Group = This group will consist of infants born to mothers belonging to the dTpa Group in study 116945 [DTPA (BOOSTRIX)-047]. All subjects in this group will receive *Infanrix hexa* co-administered with *Prevenar 13* according to the routine national immunisation schedule.

Control Group: This group will consist of infants born to mothers belonging to the Control group in study 116945 [DTPA (BOOSTRIX)-047]. All subjects in this group will receive *Infanrix hexa* co-administered with *Prevenar 13* according to the routine national immunisation schedule.

GMT = geometric mean antibody concentration calculated on all subjects

N = number of subjects with available results

n(%)=number(percentage) of subjects with antibody concentrations above the specified cut-off

95% CI = exact 95% confidence interval; LL = Lower Limit, UL = Upper Limit

Pre-Pri = blood sample to be collected before the first dose of the primary vaccination course

Post-Pri = blood sample to be collected 1 month after the last dose of the primary vaccination course

Template 13 Vaccine responses for anti-PT, anti-FHA and anti-PRN antibody concentration 1 month after the last dose of the primary vaccination course (ATP cohort for immunogenicity)

				Vaccine response			
						95% CI	
Antibody	Group	Pre-Pri* status	N	n	%	LL	UL
anti-PT	dTpa Group	S-					
		S+ (≥cut-off IU/mL)					
		Total					
	Control Group	S-					
		S+ (≥cut-off IU/mL)					
		Total					
anti-FHA	dTpa Group	S-					
		S+ (≥cut-off IU/mL)					
		Total					
	Control Group	S-					
		S+ (≥cut-off IU/mL)					
		Total					
anti-PRN	dTpa Group	S-					
		S+ (≥cut-off IU/mL)					
		Total					
	Control Group	S-					
		S+ (≥cut-off IU/mL)					
		Total					

dTpa Group = This group will consist of infants born to mothers belonging to the dTpa Group in study 116945 [DTPA (BOOSTRIX)-047]. All subjects in this group will receive *Infanrix hexa* co-administered with *Prevenar 13* according to the routine national immunisation schedule.

Control Group: This group will consist of infants born to mothers belonging to the Control group in study 116945 [DTPA (BOOSTRIX)-047]. All subjects in this group will receive *Infanrix hexa* co-administered with *Prevenar 13* according to the routine national immunisation schedule.

S- = Initially seronegative subjects (antibody concentration below assay cut-off for anti-PT, anti-FHA, anti-PRN)

S+ = Initially seropositive (antibody concentration above assay cut-off for anti-PT, anti-FHA, anti-PRN)

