Total = subjects either seropositive or ser1gative at pre-vaccination

Vaccine response to PT, FHA and PRN antigens is defined as:

For subjects with pre-vaccination antibody concentration below the assay cut-off, post-vaccination antibody concentration equal or above the assay cut-off,

For subjects with pre-vaccination antibody concentration equal or above the assay cut-off, post-vaccination antibody concentration equal or above the pre-vaccination antibody concentration

N = number of subjects with pre- and post-vaccination results available

[figure not shown]
n(%) = number(percentage) of subjects with booster response

95% CI = 95% confidence interval; LL = Lower Limit, UL = Upper Limit

*Pre-Pri = blood sample to be collected before the first dose of the primary vaccination course

Note: The assay cut-off is 2.693 IU/mL for anti-PT, 2.046 IU/mL for anti-FHA, and 2.187 IU/mL for anti-PRN.

Template 14 Reverse cumulative curve for anti-diphtheria antibody concentration before first dose and 1 month post last dose of the primary vaccination course (ATP cohort for immunogenicity)

dTpa Group = This group will consist of infants born to mothers belonging to the dTpa Group in study 116945 [DTPA (BOOSTRIX)-047]. All subjects in this group will receive *Infanrix hexa* co-administered with *Prevenar 13* according to the routine national immunisation schedule.

Control Group: This group will consist of infants born to mothers belonging to the Control group in study 116945 [DTPA (BOOSTRIX)-047]. All subjects in this group will receive *Infanrix hexa* co-administered with *Prevenar 13* according to the routine national immunisation schedule.

Pre-Pri = blood sample to be collected before the first dose of the primary vaccination course

Post-Pri = blood sample to be collected 1 month after the last dose of the primary vaccination course

Note: The groups shown in figure are indicative only. Actual groups may differ.

Template 15 Number and percentage of subjects who received study vaccine doses by vaccination group (Total vaccinated cohort)

Total number of doses received	dTpa group N =		Control group N =	
	n	%	n	%
0				
1				
2				
3				
Any				

dTpa Group = This group will consist of infants born to mothers belonging to the dTpa Group in study 116945 [DTPA (BOOSTRIX)-047]. All subjects in this group will receive *Infanrix hexa* co-administered with *Prevenar 13* according to the routine national immunisation schedule.

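### The primary pertussis vaccine response is scored against the raw pre-vaccination level, so a lower dTpa rate cannot by itself show interference; a between-group Post-Pri GMC ratio and one reading statement would help

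*SAP*

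**What the plan says.** **The rule.** SAP 4.1 and Protocol 10.5 define vaccine response to PT, FHA and PRN as appearance of antibody in initially seronegative infants and "at least maintenance of pre-vaccination antibody concentrations in subjects who were initially seropositive". The footnote to SAP Template 13 makes this operational for the seropositive: "post-vaccination antibody concentration equal or above the pre-vaccination antibody concentration". No allowance is made for decline of maternal antibody between the two samples.

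**What is expected before dose 1.** The rationale in the protocol says that maternal dTpa "vaccination during pregnancy results in high pertussis antibody concentrations in infants during the period between birth and the first vaccine dose". It adds that slightly lower responses to the primary series have been seen in such infants. Protocol 1.1 says of maternal antibody that low levels and "rapid decay of the antibodies in the infants often leave them at high risk for pertussis".

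**What the study is for.** Protocol 1.2.1 says it will help evaluate "if the presence of transplacentally transferred maternal antibodies interfere with the immune response to primary vaccination with" the hexavalent vaccine. The note under Table 22 (Protocol 10.3) says lower response rates were included in case of immune interference.

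**What is planned for reading the result.** Template 13 splits the response by Pre-Pri serostatus. Template 10 shows Pre-Pri and Post-Pri GMCs for both groups, and Template 14 gives reverse cumulative curves. SAP 11.1 computes GMC confidence intervals within each group only. SAP 7 is one sentence, saying that analyses are descriptive.

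**The concern.** A dTpa infant is likely to start from a higher level, and that level is mostly passive antibody that will have waned by the second sample. To count as a responder the infant must replace it and reach it again. A Control infant who makes the same amount of antibody faces a lower bar. The rate therefore depends on the Pre-Pri level as well as on the vaccine response.

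This bears on a primary endpoint of a study that asks about interference, and the sample-size section itself links lower rates to interference. A lower dTpa rate could be read as blunting when part or all of it reflects the starting level. The S-/S+ split does not prevent this. S+ is defined as "Initially seropositive (antibody concentration above assay cut-off for anti-PT, anti-FHA, anti-PRN", and the difference in level between the groups lies inside that stratum.

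**Working it through.** **1. The plan's own precision figures.** All 37 rows of Table 22 reproduce to 0.1 point with Clopper-Pearson limits. For evaluable numbers, 340 × 0.8 = 272 and 340 × 0.7 = 238 match; 340 × 0.9 = 306 against the stated 300.

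**2. Time between the two samples.** At the optimal intervals (Protocol Tables 6 to 9):
- 2,4,6 months: 60 + 60 + 30 = 150 days
- 2,3,4 months: 30 + 30 + 30 = 90 days
- two-dose schedules: 60 + 30 = 90 days

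For 2,4,6, SAP 5.2.3.1 allows "42-104 days from birth to visit 1, 52-78 days from visit 1 to visit 2, 52-78 days from visit 2 to visit 3", then 21 to 48 days to the Post-Pri sample. The span is therefore 52 + 52 + 21 = 125 to 78 + 78 + 48 = 204 days.

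**3. Direction.** The two-part rule is equivalent to: Post-Pri ≥ max(cut-off, Pre-Pri). If Post-Pri is unchanged, raising Pre-Pri can only lower the rate or leave it alone.

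Closed form, ignoring the cut-off, with independent log-normal levels of equal log10 SD s:

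rate = Φ[ log10(Post GMC / Pre GMC) / (s√2) ]

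Assume s = 0.4, Post-Pri GMC 50 in both groups, and Pre-Pri GMC 3 in Control and 15 in dTpa:
- Control: log10(16.67) / 0.566 = 2.16, rate 98.4%
- dTpa: log10(3.33) / 0.566 = 0.92, rate 82.2%

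The Post-Pri distributions are identical. Table 22 at 272 subjects gives 95.8 to 99.4 for 98% and 74.9 to 84.7 for 80%, so group intervals could look clearly different with no change in infant response.

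**4. Allowing for residual maternal antibody.** Post = A + Pre × 2^(−t/h), with the same vaccine-induced A in both groups. All the following are assumptions, because the documents give no values:
- GMC of A 50, log10 SD 0.3 or 0.4
- half-life h 30 or 45 days, t 90 or 150 days
- Control Pre-Pri GMC 0.05 or 0.1 of the GMC of A

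The cut-offs are those in SAP 9 (2.693, 2.046 and 2.187 IU/mL). There were 200,000 simulated infants per group per cell.

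| dTpa Pre-Pri GMC as share of GMC of A | dTpa rate, % | Control minus dTpa, points |
|---|---|---|
| 0.1 | 96.3 to 99.6 | about 0 to 3 |
| 0.2 | 89.5 to 97.4 | 2 to 9 |
| 0.3 | 82.9 to 93.7 | 6 to 16 |
| 0.5 | 71.0 to 84.4 | 15 to 28 |

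Control rates were 96.3 to 100%. Within S+ alone the gaps were nearly the same: 2 to 9, 6 to 16 and 15 to 27 points at shares 0.2, 0.3 and 0.5.

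A separate grid without residual antibody (SD 0.4 to 0.5, Post-Pri GMC 30 to 80, Control Pre-Pri GMC 3 to 6) gave gaps of about 9 to 39 points for a fivefold higher Pre-Pri GMC. The one exception to the direction was a corner case with Control Pre-Pri GMC far below the cut-off and a weak infant response, where the dTpa rate rose by at most about 0.5 point.

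**5. Sampling error.** For 98% v 96%: 1.96 × √[(0.98 × 0.02 + 0.96 × 0.04)/n] = 2.7 points at n = 300 per group and 3.1 at n = 238. The smallest gaps could not be seen.

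**6. Does a Post-Pri GMC ratio (dTpa/Control) separate the two explanations?** On the grid in step 4, at shares 0.1 to 0.5:
- No interference: 1.00 to 1.20 at 90 days, 0.99 to 1.09 at 150 days.
- dTpa vaccine-induced response halved: 0.51 to 0.70 at 90 days, 0.50 to 0.59 at 150 days.
- Milder interference growing with Pre-Pri (A falling as Pre-Pri to the power −0.2 or −0.3 above the PT cut-off): 0.58 to 1.00, mostly below 1. It reaches 1.00 at share 0.1, where Control can have the same Pre-Pri level.

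The 95% CI multiplies or divides the ratio by 10^(1.96 × s × √(2/n)). At n = 238 per group this is 1.13 for s = 0.3 and 1.18 for s = 0.4, so a halving would be plain.

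**The case against.** **No analysis is wrong.** The study has no hypothesis, margin or power calculation, and every analysis is descriptive. The harm is a possible misreading, which the study report could also address. This stands, and is why the point is only an improvement to consider.

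**Most of the evidence is already planned.** Templates 10, 13 and 14 show Post-Pri levels by group, and the overall ratio and its CI could be derived from the planned GMCs, intervals and numbers of subjects. This is largely right. What is missing is the estimate itself and a prior statement that it guides the reading of the primary rate.

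**A reader might infer that a lower dTpa rate would be pure artefact.** The documents do not support that. The protocol reports slightly decreased responses after maternal dTpa, whereas the gaps in the table assume none. A lower rate may be a mixture.

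**A reader might infer that the plan as a whole gives no guidance.** That cannot be asserted. Protocol 10.9, on interpretation, is in the table of contents, but its text was not available here. The silence is that of SAP 7.

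**A reader might want the response tabulated by Pre-Pri band.** This conditions on the proposed cause of interference. In simulation the within-band gaps were at most about 3 points without interference and about 5 with it, so the table could falsely reassure.

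**A reader might want the schedules separated**, because SAP 6.3.2 pools "3 doses i.e. 2,3,4 months combined with 2,4,6 months" and so mixes 90-day and 150-day infants. But the pooled stratum is already 457/528 = 87% on 2,4,6, and all 71 infants on 2,3,4 are in Czechia, so interval is confounded with country. With about 36 per group (equal split assumed), the ratio's 95% CI factor would be about 1.4 to 1.55, larger than the residual-antibody effect of at most 1.20.

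**Conclusion.** The point holds as a matter of interpretation, at the level of a cheap improvement. The direction (dTpa at or below Control with the same vaccine-induced response) follows from the definition and the protocol's own expectations, apart from the trivial corner case. The size rests wholly on assumed GMCs, SDs and half-lives. It is negligible if vaccine-induced levels far exceed Pre-Pri levels in both groups, and more than 20 points if dTpa Pre-Pri levels are around half the vaccine-induced level. The primary pertussis response rate therefore cannot by itself answer the interference question. The Post-Pri GMC ratio helps, although residual maternal antibody can raise it slightly.

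It would go too far to conclude that the endpoint is invalid or should be replaced. It is computed as defined and is a legitimate descriptive measure.

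**What to change.** Keep the primary endpoint as defined.

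1. **SAP 6.3.2:** add, as a supportive descriptive analysis, the overall dTpa/Control Post-Pri GMC ratio with 95% CI for PT, FHA and PRN.
2. **SAP 7:** add a statement such as: *A lower PT, FHA or PRN vaccine response rate in the dTpa Group is not by itself evidence of interference, because the rate depends on the Pre-Pri concentration; it is read together with the Post-Pri GMC ratio, which residual maternal antibody can raise slightly.*

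The cost is three supportive rows and one sentence, with no new data. The downsides are that the primary rate carries a caveat and that the ratio can modestly understate blunting, mainly when the samples are about 90 days apart. Both changes should be made before results by group are interpreted, so that the reading is set in advance.
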